4.3 Visit schedule and assessments 4.3.1 Evaluation and Visit Schedule (Table 19)

Examination	Screening	Cycle 1		Cycle 2		Cycle 3 to Cycle n					
Day of Cycle	-21	1 (Baseline)	15	1	15	3	4	5	6	7	
Informed consent	X										
Medical History	Х										
Inclusion/ exclusion criteria	X										
Serum pregnancy test (with 72 hours of 1 st treatment for WOCBP)	As clinically indicated.										
Urinalysis	Х										
Vital signs	Х	Х	Х	Х	Х	Х	Х	Х	Х	Х	Х
Physical examination (including skin rash assessment)	Х	X		Х		X	Х	X	Х	X	Х
Performance Status ECOG	Х	Х		Х		Х	Х	Х	Х	Х	Х
Neuro-psychiatric assessment (self-rating mood questionnaire GAD and PHQ)	х	Х	X	X	X	Х	Х	X	Х	Х	Х
Examination	Screening	Cycle 1		Cycle 2		Cycle 3 to Cycle n					
Day of Cycle	-21	1 (Baseline)	15	1	15	3	4	5	6	7	
12-lead ECG*	Х	As clinically indicated.									
Chest X-Ray (if locally advanced disease only)	Х	Every 8 weeks from start of treatment until progression as per RECI									

Radiological tumor	Х					Х		Х		Х	
assessment/response											
assessment (CT or MERI											
Scans if no clinically											
visible)**											
Hematology*	Х	X	X	X	Х	Х	Х	Х	Х	Х	
Serum Chemistry*	Х	Х	Х	Х	Х	Х	Х	Х	Х	Х	
Coagulation Profile*	Х			Х			Х		Х		
Fasting plasma glucose*	Х	Х	Х	Х	Х	Х	Х	Х	Х	Х	
HgA1C*	X					X			X		
Tumor biopsy for biomarkers ³	Х					Х			Х		

^{*} Can use screening if w/in 72 hours of baseline.

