As more and more patients with BCCs are treated with Smoothened inhibitors, the presence of resistant tumor populations has become a critical issue. This pilot study will provide vitally important information regarding the potential of dual treatment with PI3K inhibitor (buparlisib) PLUS Smoothened inhibitor (Sonidegib) to address resistance.

It is currently unclear whether the clinical efficacy of combination therapy (termed LB therapy) is more pronounced if it is instituted at the outset versus after resistance is clinically apparent.

2 Study objectives

Primary Objective

To estimate the overall response rate (ORR) of sonidegib in combination with buparlisib (hereby referred to as "LB therapy") for patients with locally advanced or metastatic BCC in Smoothened inhibitor naive patients (Cohort 1) and those whose disease is refractory or relapsed on Smoothened inhibitor monotherapy (Cohort 2).

Secondary Objectives

- ◆◆ To estimate the median duration of response, on or after LB therapy
- ◆◆ To assess the safety and tolerability of LB therapy
- ◆◆ To assess the histopathologic effect of LB therapy in tumor biopsies obtained at baseline and following 12 weeks of treatment
- ◆◆ To assess the effect of LB therapy on gene expression including Hedgehog pathway and PI3K pathways.
- ◆◆ To assess correlation between gene mutations in Smoothened, Sufu, PTCH, Gli1,2 and gene expression profiles and response to LB therapy

3 Exploratory Investigational plan

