4.3.5.5 Neuropsychiatric assessments

Patient self-rating mood questionnaires for anxiety and depression (PHQ-9, GAD-7) will be applied at:

- **♦♦** Screening
- ◆◆ Days 1 and 15 of Cycle 1
- ◆◆ Day 1 and 15 of Cycle 2
- •• Day 1 of Cycle 3 and subsequent cycles (only for patients who have not shown mood alterations during the first 2 cycles, patients who did should continue to fill out the questionnaire on a weekly base).
- **♦♦** End of Study treatment

Additional assessments may be done according to the clinical judgment of the Investigator. Symptomatic patients (\geq CTCAE Grade 1) must continue with questionnaires on a weekly basis while active on the treatment portion of the study. Instructions on how to instruct the patient to complete the questionnaires as well as how to determine the scores will be provided together with each instrument. This will be done as an online HIPPA compliant survey tool through Stanford.

4.3.5.6 **ECG/ECHO**

A standard 12 lead ECG is to be performed at screening and as clinically indicated. An echocardiogram (ECHO) or MUGA will be performed to assess eligibility. ECHO/MUGA will be repeated at Cycle 4 and then every 4th cycle thereafter.

4.3.5.7 **Performance status**

Performance status will be assessed at screening and per the visit schedule. ECOG will be used for assessment (See Appendix A).

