4.3.5.8 Special tests

Chest X-ray

Will be performed at baseline and every 8 weeks for monitoring per standard protocol.

CT scan

Will be performed at baseline, at 4 weeks and every 8 weeks thereafter for tumor assessment of non-visible tumors per RECIST 1.1 protocol. If CT scans show stability after cycle 4, then CT scan to be performed every 12 weeks instead.

Biomarkers

- ◆◆ Tissue samples at baseline, week 12 and 24 (or EOT, whichever occurs first) will be taken and sent for whole exome sequencing, gene expression profiling and immunohistochemistry. Whole exome sequence will include interrogation for DNA mutations in the tumor and peripheral blood. Gene expression analysis will identify increases or decreases in pathways including Hedgehog and PI3K. Immunohistochemistry to quantify protein levels of Gli 1,2, Ptch 1,2, PI3K in semi-quantitative fashion will be performed to confirm expression analysis results.
- ♦♦ Whole exome sequencing and gene expression analysis may identify novel resistance mechanisms in these BCCs that would be useful to inform future clinical trials

5 Investigational agent sampling and shipping information

[name], or her designated associate will receive study medications at the Stanford Investigational Pharmacy, Redwood City, CA.

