5.2.1 Buparlisib

Novartis supplies buparlisib as 10-mg and 50-mg hard gelatin capsules. buparlisib will be administered orally once a day, as part of each 28-day cycle. Medication labels comply with the legal requirements of each country and will be printed in the local language. The storage conditions for study drug will be described on the medication label.

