6.1.1 Variables

- overall response rate (ORR) of LB therapy for patients with locally advanced or metastatic BCC in Smoothened inhibitor naive patients (Cohort 1) and those whose disease is refractory or relapsed on Smoothened inhibitor monotherapy (Cohort 2).
- median duration of response, on or after LB therapy
- frequency and severity of adverse events, including serious adverse events of LB therapy
- semi-quantitative evaluation of immunostaining for biomarkers including Gli 1, 2, PTCH, Sufu, Smoothened, PI3K markers and gene expression profiles at baseline and following 12 weeks of treatment

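### Table 19 marks the on-treatment biopsies at Cycles 3 and 6 with no day; read as Day 1 visits these are weeks 8 and 20, not the weeks 12 and 24 stated elsewhere.

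*Combined protocol and SAP*

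**What the plan says.** Five places bear on when tumor tissue is taken.

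- **Table 19, Section 4.3.1.** The row "Tumor biopsy for biomarkers" is marked at Screening, Cycle 3 and Cycle 6. The later columns sit under "Cycle 3 to Cycle n" and carry cycle numbers only. The row has a footnote mark, and the only footnote about tissue gives baseline, week 12 and week 24 or end of treatment.
- **Section 4.3.5.8, Biomarkers.** The same timing in the text: "Tissue samples at baseline, week 12 and 24 (or EOT, whichever occurs first) will be taken".
- **Section 2, Secondary Objectives.** The histopathology objective uses "tumor biopsies obtained at baseline and following 12 weeks of treatment". The objectives on gene expression, and on its correlation with response, name no time point.
- **Section 6.1.1.** The biomarker variable covers immunostaining and "gene expression profiles at baseline and following 12 weeks of treatment".
- **Cycle length and visit day.** Section 5.2.1 has drug given "as part of each 28-day cycle". Section 4.3.5.5 places the mood questionnaires on "Day 1 of Cycle 3 and subsequent cycles", and Section 4.1.2.3.3 describes the later scheduled visits in the same way.

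**The concern.** The calendar is what staff use to book procedures, and its marks do not obviously give the weeks that the text requires. If the Cycle 3 and Cycle 6 columns are Day 1 visits like the others, both on-treatment biopsies come 4 weeks before the stated times.

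The first biopsy matters most. Twelve weeks is the only on-treatment tissue time point named in an objective or variable, and Section 7.1.1 assesses response after 12 weeks of treatment. If some patients are sampled at week 8 and others at week 12, the change from baseline mixes two exposures, and expression at week 8 may be related to a response read 4 weeks later. The study plans 12 patients per cohort and takes tissue only where the tumor is accessible, so a mistimed invasive sample is hard to make good.

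**Working it through.** **Inputs.** Cycle length 28 days (Sections 5.2.1 and 5.2.2). Biopsy marks at Screening, Cycle 3 and Cycle 6 (Table 19). Stated biopsy times weeks 12 and 24 (Table 19 footnote, Section 4.3.5.8). Imaging marks at Cycles 3, 5 and 7 (Table 19), with an 8-week interval in the radiology footnote.

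**Column check.** The vital-signs row fills all 11 data columns: Screening, Cycle 1 Days 1 and 15, Cycle 2 Days 1 and 15, Cycles 3 to 7, and one unlabelled column. Against that row, the biopsy marks fall in columns 1, 6 and 9, which are Screening, Cycle 3 and Cycle 6.

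**Formulas.** Day 1 of cycle c is study day 28(c − 1) + 1, with 28(c − 1)/7 weeks completed. The last day of cycle c is study day 28c, with 28c/7 weeks completed.

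| Cycle | Day 1: study day | Weeks completed | Last day: study day | Weeks completed |
|---|---|---|---|---|
| 3 | 57 | 8 | 84 | 12 |
| 4 | 85 | 12 | 112 | 16 |
| 6 | 141 | 20 | 168 | 24 |
| 7 | 169 | 24 | 196 | 28 |

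**Reproducing the stated weeks.** On Day 1, Cycles 3 and 6 give weeks 8 and 20, so weeks 12 and 24 are not reproduced. On the last day of the cycle they are reproduced exactly.

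**Which reading the table uses.** Imaging at Cycles 3, 5 and 7 gives weeks 8, 16 and 24 on Day 1, which agrees with the 8-week interval in the footnote. At the end of the cycle it gives weeks 12, 20 and 28, so the first on-treatment scan would come at week 12. The mood questionnaires share these columns and are fixed at Day 1. Sections 5.2 and 5.2.2 dispense drug at the start of each cycle. The end of Cycle 3 (day 84) is one day before Cycle 4 Day 1 (day 85), and Cycle 4 has its own column with no biopsy mark. The same holds for Cycles 6 and 7. No end-of-cycle visit is scheduled.

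**Size of the gap.** 12 − 8 = 4 weeks, or 4/12 = one third of the intended exposure, at the first on-treatment biopsy. 24 − 20 = 4 weeks, or 4/24 = one sixth, at the second.

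**Can a window absorb it?** The ±7 days in the radiology footnote, if applied to biopsies, reaches weeks 7 to 9 and 19 to 21. It does not reach week 12 or week 24.

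**The case against.** The strongest reply is that weeks 8 and 20 are never printed. Table 19 gives no day for Cycle 3 onward, and the ends of Cycles 3 and 6 are exactly weeks 12 and 24, so the marks may have been meant that way. The CT schedule in Section 4.3.5.8 (week 4, then every 8 weeks: 4, 12, 20, 28) partly fits an end-of-cycle reading. It also disagrees with the radiology footnote, which weakens imaging as evidence for Day 1. The biopsy row's own footnote already states weeks 12 and 24, so anyone who reads it has the intended times.

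Much of this stands. Day 1 is an inference, and the footnote makes week 12 available to a careful reader. It does not remove the conflict. An end-of-cycle biopsy has no visit to attach to, the adjacent Day 1 columns that would serve are unmarked, and Table 19 has no week-4 imaging mark to match the CT text. Whichever timing was meant, the table needs an edit.

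Three stronger readings are tempting, and the documents do not support them.

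- **That the calendar makes the trial miss week 12.** This requires following the mark at a Day 1 visit and overlooking the footnote. The study is single-center (Section 3.1), so any mixture would arise between patients or staff, not between sites.
- **That week-24 tissue serves no objective.** The expression and correlation objectives, and the matching variables in Section 6.2, name no time point and can use it.
- **That most acquired resistance falls after the last biopsy.** Section 1.1 gives about 20% of responders resistant after 1 year on Smoothened-inhibitor treatment, with no time distribution. If that means 20% by one year at a constant hazard (an assumption), 1 − 0.8^(24/52) = 9.8% occurs by week 24, about half the one-year total. Patients who stop before week 24 give tissue at end of treatment, and Cohort 2 enters already refractory or resistant. Moving the third sample to progression would be a separate trade-off, and it is not part of this point.

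**Conclusion.** The point holds as an internal inconsistency in the schedule. The biopsy marks in Table 19, read as Day 1 visits, fall at weeks 8 and 20. This conflicts with the tissue footnote and Section 4.3.5.8 for both samples and, for week 12, with the histopathology objective and the Section 6.1.1 biomarker variable. The possible error is 4 weeks per on-treatment biopsy.

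The conclusion rests on two things: the 28-day cycle, which is stated, and Day 1 visits from Cycle 3 on, which are stated for the questionnaires and scheduled visits but only inferred for biopsies. How many patients would be mistimed cannot be known from the documents. The planned 24 is a ceiling on planned accrual, reached only if every tumor is accessible and the marks are followed throughout. The correction is worth making because it protects the one on-treatment tissue time point that an objective names.

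**What to change.** Amend the biopsy row of Table 19 in one of two ways.

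1. Move the marks from Cycles 3 and 6 to Cycle 4 Day 1 (study day 85, week 12) and Cycle 7 Day 1 (study day 169, week 24).
2. If end of cycle was intended, keep the marks and print in the row that they mean the end of Cycle 3 (week 12) and the end of Cycle 6 (week 24), with a visit to carry them.

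In either case, state a window for biopsies, since the ±7 days appears only in the radiology footnote, and keep the row, its footnote and Section 4.3.5.8 in the same terms. If patients have already been biopsied, record the actual study day of each sample so that the paired analysis can report exposure.

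The cost is a one-row amendment. The first option adds no visit. The second needs a visit one day before an existing one. Neither changes the number of biopsies.

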4.3.2 Efficacy assessments

Efficacy will be assessed on the basis of clinical examination using calipers if the target tumor is visible on the skin. If it is not visible on the skin tumor imaging will be used to assess the single longest diameter for the basis of efficacy assessment. (see 4.3.1 Evaluation and Visit Schedule (Table 19). Tumor response by RECIST 1.1 criteria will be used for evaluation.

4.3.3 Safety assessments

Patients enrolled in this clinical trial will be evaluated clinically and with standard laboratory tests before and at regular intervals during their participation in this study (see Study Calendar). Safety evaluations will consist of tumor assessments performed every 4 weeks, routine hematology, comprehensive metabolic profiles, EKGs and urinalysis.

^{**}Screening radiological assessments should be performed within 4 weeks of the first dose. Radiological tumor assessment should be performed at baseline within 28 days before start of treatment and subsequently every 8 weeks, until progression of disease or end of treatment. If stable after cycle 4, then CT scan to be performed every 12 weeks instead. All assessments should be performed within ± 7 days of the scheduled day of assessment. The assessment at the EOT visit is only to be performed if the prior assessment occurred ≥ 21 days before.

Tissue samples at baseline, week 12 and 24 (or EOT, whichever occurs first) will be taken and sent for whole exome sequencing, gene expression profiling and immunohistochemistry if accessible to tumor biopsy.

To date, Sonidegib has been shown to be well-tolerated in early phase clinical studies with the most common side effects consisting of fatigue, nausea, vomiting, anorexia, muscle cramps, and dysgeusia (5). To date, the most common adverse events of patients on buparlisib ($\geq 15\%$), regardless of grade and causality, reported in any treatment cycle were decreased appetite (45.5%), nausea (39.4%), constipation, diarrhea, fatigue (each 31.8%), rash (30.3%), hyperglycemia (27.3%), asthenia (25.8%), abdominal pain, vomiting (each 22.7%), anxiety (21.2%), depression (19.7%), mucosal inflammation, pruritus (each18.2%), dyspnea (16.7%), AST increase, dry skin, dyspepsia, pyrexia, and somnolence (each 15.2%), data provided by Novartis.

It is possible that the combination of the two medications, Sonidegib and buparlisib may lead to additive or synergistic side effects. Independently, both medications are known to cause frequent gastrointestinal side effects such as nausea and vomiting and the concomitant administration of both may compound these side effects.

All adverse events will be attributed to LB therapy unless they can be clearly attributed to progression or to another clearly identified etiology by the investigator. Adverse events will be graded according to the National Cancer Institute Common Terminology Criteria for Adverse Events Version 3.0.

Intolerable toxicities are defined as new (not present at baseline) Grade 3 or 4 adverse events deemed to be related to LB therapy that are life threatening or irreversible, and when (in the opinion of the investigator) the risks outweighs the benefit of continued treatment.

Women of childbearing potential will be required to have a negative serum pregnancy test at screening, urine pregnancy test on Day 1 and every 4 weeks while on study. Women of childbearing potential or male patients with female partners of childbearing potential are required to use a highly reliable method of contraception, and for 12 weeks after discontinuation of LB therapy. Patients must agree not to donate bodily fluids for 12 months after discontinuation of LB therapy.

Safety assessments will consist of monitoring and recording all adverse events and serious adverse events, the regular monitoring of hematology, blood chemistry and urine values, regular measurement of vital signs and the performance of physical examinations. These assessments should be performed within ±2 days of the scheduled day of assessment except for adverse events that will be evaluated continuously through the study. Safety and tolerability will be assessed according to the NIH/NCI CTC (http://ctep.cancer.gov/protocolDevelopment/electronic applications/ctc.htm#ctc 40).

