- 24. Women who are pregnant or breast feeding or adults of reproductive potential not employing an effective method of birth control. Double barrier contraceptives must be used through the trial by both sexes. Oral, implantable, or injectable contraceptives may be affected by cytochrome P450 interactions, and are therefore not considered effective for this study. Women of child-bearing potential, defined as sexually mature women who have not undergone a hysterectomy or who have not been naturally postmenopausal for at least 12 consecutive months (ie, who has had menses any time in the preceding 12 consecutive months), must have a negative serum pregnancy test ≤ 72 hours prior to initiating treatment.
 - ♦♦ Women are considered post-menopausal and not of child bearing potential if they have had 12 months of natural (spontaneous) amenorrhea with an appropriate clinical profile (eg, age appropriate, history of vasomotor symptoms) or six months of spontaneous amenorrhea with serum FSH levels > 40 mIU/mL (for US only: and estradiol < 20 pg/mL) or have had surgical bilateral oophorectomy (with or without hysterectomy) at least six weeks ago. In the case of oophorectomy alone, only when the reproductive status of the woman has been confirmed by follow up hormone level assessment is she considered not of child bearing potential.
 - •• Women of child-bearing potential, defined as all women physiologically capable of becoming pregnant, must use highly effective contraception during the study and through 20 months after the final dose of study treatment. For males with partners with childbearing potential, highly effective contraception is required for 6 months. The highly effective contraception is defined as either:
- I. True abstinence: When this is in line with the preferred and usual lifestyle of the subject. Periodic abstinence (eg, calendar, ovulation, symptothermal, post-ovulation methods) and withdrawal are not acceptable methods of contraception.
- II. Sterilization: have had surgical bilateral oophorectomy (with or without hysterectomy) or tubal ligation at least six weeks ago. In case of oophorectomy alone, only when the reproductive status of the woman has been confirmed by follow up hormone level assessment.
- III. Male partner sterilization (with the appropriate post-vasectomy documentation of the absence of sperm in the ejaculate). For female subjects on the study, the vasectomised male partner should be the sole partner for that patient.

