- IV. Use of a combination of any two of the following (a+b):
 - a. Placement of an intrauterine device (IUD) or intrauterine system (IUS)
 - b. Barrier methods of contraception: Condom or Occlusive cap (diaphragm or cervical/vault caps) with spermicidal foam/gel/film/cream/vaginal suppository

- •• Oral contraception, injected or implanted hormonal methods are not allowed as buparlisib potentially decreases the effectiveness of hormonal contraceptives.
- ◆◆ Fertile males, must use highly effective (double barrier) methods of contraception (eg, spermicidal gel plus condom) for the entire duration of the study, and continuing using contraception and refrain from fathering a child for 6 months following the study drug. A condom is required to be used also by vasectomized men as well as during intercourse with a male partner in order to prevent delivery of the study treatment via seminal fluid. Female partner of male study subject should use highly effective contraception during dosing of any study agent and for 16 weeks after final dose of study therapy.

Note: Hormonal contraception methods (eg, oral, injected, implanted) are not allowed as it cannot be ruled out that the study drug decreases the effectiveness of hormonal contraception.

Note: Woman are considered post-menopausal and not child bearing potential if they have had 12 months of natural (spontaneous) amenorrhea with an appropriate clinical profile (eg, age appropriate, history of vasomotor symptoms) or six months of spontaneous amenorrhea with serum FSH levels > 40 mIU/ mL and estradiol < 20 pg/mL or have had surgical bilateral oophorectomy (with or without hysterectomy) at least six weeks ago. In the case of oophorectomy alone, only when the reproductive status of the woman has been confirmed by follow up hormone level assessment is she considered not of child bearing potential

- 25. Known diagnosis of human immunodeficiency virus (HIV) infection, Hepatitis B or Hepatitis C
- 26. History of another malignancy within 3 years, except cured basal cell carcinoma of the skin or excised carcinoma in situ of the cervix
- 27. Patient is unable or unwilling to abide by the study protocol or cooperate fully with the investigator

4 Treatments

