 14. Women of child-bearing potential, defined as all women physiologically capable of becoming pregnant, including women whose career, lifestyle, or sexual orientation precludes intercourse with a male partner and women whose partners have been sterilized by vasectomy or other means, UNLESS they are using two birth control methods. The two methods can be a double barrier method or a barrier method plus a hormonal method. Adequate barrier methods of contraception include: Diaphragm, condom (by the partner), intrauterine device (copper or hormonal), sponge or spermicide. Hormonal contraceptives include any marketed contraceptive agent that includes an estrogen and/or a progestational agent. Reliable contraception should be maintained throughout the study and for 3 months after study drug discontinuation. 	

15. Uncontrolled medical medical problems including acute or chronic liver disease, renal disease or pancreatitis, diarrhea >CTCAE grade 2, active cardiac disease, uncontrolled diabetes, chronic steroids or other immunosuppressive agents		
16. Patients who have taken herbal medications and certain fruits within 7 days prior to starting study drug. Herbal medications include, but are not limited to St. John's Wort, Kava, ephedra (ma huang), dehydroepiandrosterone (DHEA), gingko biloba, yohimbe, saw palmetto, and ginseng. Fruits include the CYP3A inhibitors Seville oranges, grapefruit, pummelos, or exotic citrus fruits.		
17. Patients who are currently treated with drugs known to be moderate and strong inhibitors or inducers of isoenzyme CYP3A, and the treatment cannot be discontinued or switched to a different medication prior to starting study drug. Please refer to Table 15 for a list of prohibited inhibitors and inducers of CYP3A (Please note that co-treatment with weak inhibitors of CYP3A is allowed).		
18. Patients who have received any continuous or intermittent small molecule therapeutics (excluding monoclonal antibodies) ≤ 5 effective half lives prior to starting study drug or who have not recovered from side effects of such therapy		
19. Use of statin drugs or other medications known to associate with rhabdomyolysis. These drugs must be discontinued at enrollment		

20. Patients who have received wide field radiotherapy ≤ 4 weeks or limited field radiation for palliation ≤ 2 weeks prior to starting study drug or who have not recovered from side effects of such therapy	

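### Section 4.3.3 sets 12 weeks of contraception after treatment where Section 3.2.2.2 requires 20 months (women) and 6 months (men); the Appendix B form gives 3 months and departs from Section 3.2.2 on other criteria

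*Combined protocol and SAP*

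**What the plan says.** Three places in the combined protocol and SAP set contraception after the last dose.

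- **Section 4.3.3** applies one rule to women of childbearing potential and to men with partners of childbearing potential: they "are required to use a highly reliable method of contraception, and for 12 weeks after discontinuation of LB therapy".
- **Section 3.2.2.2, exclusion 24** sets a different rule for each group. Women of child-bearing potential "must use highly effective contraception during the study and through 20 months after the final dose of study treatment". For men with such partners, "highly effective contraception is required for 6 months"; a later bullet gives the starting point, telling fertile men to "refrain from fathering a child for 6 months following the study drug". Female partners of male patients should use "highly effective contraception during dosing of any study agent and for 16 weeks after final dose of study therapy".
- **Appendix B, exclusion 14**, which concerns women only: "Reliable contraception should be maintained throughout the study and for 3 months after study drug discontinuation". The form has no contraception item for male patients.

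The texts also disagree on method. Appendix B says: "The two methods can be a double barrier method or a barrier method plus a hormonal method". Section 3.2.2.2 says: "Oral contraception, injected or implanted hormonal methods are not allowed", because buparlisib may make them less effective.

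Appendix B is the form on which a subject is declared eligible or ineligible. Several of its laboratory entries differ from Section 3.2.2; they are set out in the check below.

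**The concern.** Section 1.4.4 states that sonidegib is teratogenic, so the length of contraception after treatment is a safety instruction. Site staff who counsel from Section 4.3.3 would give a much shorter period than staff who counsel from Section 3.2.2.2. No scheduled contact would bring this to light. Adverse events are followed for 28 to 30 days after the last dose (Sections 4.1 and 4.1.1), pregnancy tests run only while the patient is on study (Sections 4.3.3 and 4.3.5.2), and pregnancy reporting is written for patients on study treatment (Section 4.3.5.1). Section 4.3.3 itself bars donation of body fluids for 12 months while ending contraception at 12 weeks.

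The second issue is the form. A patient cleared on Appendix B alone could enter with liver tests that Section 3.2.2.1 does not accept, or without several limits having been checked. Section 1.5.2.2.1 explains that buparlisib protocols adopted conservative selection criteria because of liver findings, so the tighter limits have a stated purpose.

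**Working it through.** The plan gives no figure of its own to reproduce. The check sets the texts side by side, with unit conversion at 30.44 days per month (an assumption, the average calendar month).

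**Duration after the last dose**

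| Group | Section 3.2.2.2 | Section 4.3.3 | Appendix B |
|---|---|---|---|
| Women of childbearing potential | 20 months | 12 weeks | 3 months |
| Men | 6 months | 12 weeks | no item |
| Female partners of male patients | 16 weeks | no rule of their own | no item |

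- Women: 20 × 30.44 / 7 = 87.0 weeks. 87.0 − 12 = 75.0 weeks, and 75.0 × 7 / 30.44 = 17.2 months. Against the form, 20 − 3 = 17 months.
- Men: 6 × 30.44 / 7 = 26.1 weeks. 26.1 − 12 = 14.1 weeks.
- Female partners: the 12 weeks set for the man is 16 − 12 = 4 weeks shorter than the partner rule.

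**Laboratory limits.** Inclusion items 9a–c, 10–18 and 20, with exclusion item 5, give 14 limits in Section 3.2.2.

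| Limit | Section 3.2.2 | Appendix B |
|---|---|---|
| ANC, platelets, creatinine | as stated | same |
| ALT/AST | normal; 3.0 x ULN with liver metastases | 2.5 x ULN; 5 x ULN with liver metastases |
| Bilirubin | normal; 1.5 x ULN with liver metastases; Gilbert rule | 1.5 x ULN for all |
| Hemoglobin | above 9 g/dL, or at least LLN | at least 9 g/dL (trivial difference) |
| CK | above ULN excluded | a 1.5 x ULN ceiling and a CK above ULN line, both in the inclusion list |
| Calcium, magnesium, potassium, amylase, lipase, fasting glucose, INR | limits set | absent |

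The tally is 3 the same, 4 different (hemoglobin trivially) and 7 absent: 3 + 4 + 7 = 14. If the second CK line is a misplaced exclusion, the form's working CK limit equals the body's and the tally becomes 4, 3 and 7.

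**The other direction.** Some checks appear on the form but not in the criteria lists of Sections 3.2.2.1 and 3.2.2.2:
- an exclusion from Cohort 1 for prior Smoothened-inhibitor therapy (form exclusion 1);
- histologic diagnosis and measurable disease for every patient (form inclusions 3 and 5), where the body requires histologic confirmation and measurability only for metastatic disease;
- neuromuscular disorders (form exclusion 8);
- narrow-therapeutic-index drugs metabolised by CYP2B6 or CYP2C9 (form exclusion 12).

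**The case against.** The strongest defence of 12 weeks is pharmacokinetic. Section 1.4.7.2.1 gives a median effective half-life for sonidegib of 11 days, and Section 1.4.7.1 a range up to 14 days. Five half-lives are 55 to 70 days, inside the 84 days of Section 4.3.3. That stands as a reason not to call 12 weeks proven wrong. It does not validate it: the protocol never makes the argument, and Section 1.4.7.1 says that an accurate terminal half-life cannot be calculated by the non-compartmental approach. It also leaves the contradiction in place.

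A second defence is Section 3.2.2, which requires the investigator to review baseline results against all criteria before enrollment. This limits the harm from the form. It does not settle the contraception conflict, because both texts are in the body and the issue arises after treatment.

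A third is that the form is not looser throughout. It is stricter for Gilbert syndrome, equal on bilirubin with liver metastases, and gives no exemption for abstinence or a vasectomised partner, both of which Section 3.2.2.2 accepts. That is correct.

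Finally, Section 3.2.2.2 is not a clean template. It first asks for double-barrier methods from both sexes and then accepts abstinence, sterilization or a vasectomised partner. Copying it over the form would also delete the form-only checks, including the one that keeps Cohort 1 naive. Both objections stand and shape the fix.

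**Conclusion.** The contraception conflict is real, within the body of the protocol, and needs correcting. Against Section 3.2.2.2, following Section 4.3.3 ends contraception about 75 weeks early for women and 14 weeks early for men; following the form ends it 17 months early for women. The form differences on ALT/AST, on bilirubin without liver metastases and on the seven absent limits are also real, but secondary.

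A reader might infer more than the documents support:
- *That 12 weeks is unsafe.* No basis is given for any of the durations. Treating Section 3.2.2.2 as the default is an assumption, resting on its being the eligibility section and the longer, more cautious rule.
- *That patients were told the wrong period.* The consent pages are not available here.
- *That ineligible patients were enrolled.* It is possible, but Section 3.2.2 requires review against the body criteria.
- *That the form firmly contradicts the body on CK.* The entry is unclear, and the CK above ULN line is probably a misplaced exclusion. Nor is a CK hazard shown at 200 mg daily: Table 1 lists no cycle 1 dose-limiting CK event in 5 + 6 + 4 = 15 patients at 100 to 400 mg once daily, though that is a small sample.

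The point concerns safety and eligibility. It does not touch the sample size or the planned analysis.

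**What to change.** 1. The sponsor confirms one post-treatment duration per group, including whether 6 months for men and 16 weeks for their partners are both intended. Unless it documents a reason otherwise, put the Section 3.2.2.2 periods (20 months, 6 months, 16 weeks) into Section 4.3.3 and Appendix B.
2. In Section 3.2.2.2, resolve the double-barrier rule for everyone against the alternatives accepted after it.
3. On the form, bar oral, injected and implanted hormonal methods and add a contraception item for men.
4. On the form, set ALT/AST and bilirubin to the Section 3.2.2.1 limits, move CK above ULN to the exclusions, delete the 1.5 x ULN line, and add the seven missing limits.
5. Keep the form-only safeguards listed above and add them to Section 3.2.2. The Cohort 1 item names only inhibitors other than sonidegib; word it to match the naive population in Section 3.2.1.
6. For any patients already enrolled, check files against the reconciled criteria, record deviations, confirm the contraception period they were given, and re-counsel them.

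The cost is a protocol amendment, a revised form, the file check and re-counselling, and possibly slightly slower accrual. No new tests are needed, because Table 19 and Section 4.3.5.2 already include chemistry, fasting glucose and coagulation at screening. The analysis does not change.
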